Provisions for post-trial care Patients that are enrolled into the study are covered by indemnity for negligent harm through the standard NHS Indemnity arrangements from Gateshead health trust. Following the procedure participants will be offered the opportunity to ask the team any questions. They will be provided with contact details for the study team if they have any concerns when they have left following the procedure.

Additional patient follow up will not routinely be performed as part of the study. Any follow up will be as per standard colposcopy practice.

Outcomes

[figure not shown]
Primary outcome

- To determine any change in anxiety experienced by people with a cervix attending for outpatient colposcopy as measured by STAI (state trait anxiety index) in both the intervention arm and the control arm. Pre procedure paper questionnaires will be conducted to establish a baseline anxiety measure for patients. The comparison will be performed from the post procedure paper questionnaires from both arms of the study.

Secondary outcomes

- To determine any change in pain experience by people with a cervix attending for outpatient colposcopy as measured by a numerical rating scale (NRS) in both the intervention arm and control arm via paper questionnaires.
- Understanding the acceptability and effectiveness of VR interventions within the procedural groups and how these might vary as a function of different patient demographics.
- Feasibility and acceptance of intervention from clinicians' perspective
- Does the introduction of VR have an impact on patients' attendance to follow up appointments?

Participant timeline

Sample size

The sample size calculation was run using the packages pwr and pwrss within R. For the calculation the significance level of 0.05 and power of 0.8 were used along with a Cohen's d of 0.5. Two different types of outcome variables will be used so the calculations used are based on ANCOVA (continuous) and the Mann-Whitney test (ordinal). Both results suggest a sample size of 64 participants in each group (128 in total). We have added on a 10% drop out rate which brings the total sample size to 141.

Assignment of interventions

Sequence generation and concealment mechanism

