Participants will complete a questionnaire (Appendix 6a) with STAI questions prior to randomisation to get a baseline anxiety level. This will be compared to the post procedural questionnaire (Appendix 6b) with the same questions to compare the actual anxiety levels during the procedure. Comparison will be made between the two arms.

Secondary Outcome

Pain reduction: Pain scores will be measured by a Numeric Rating Scale (NRS) from 0 through to 10. 0 represents “no pain” and 10 represents “worst pain imaginable”. This will be shown alongside a visual analogue scale (VAS) of pain on animated faces. This is a validated measure for pain, is easy to use, has high compliance rates and detects meaningful change. (29,30,31) Participants will be asked to state the “maximum pain felt, if only for one moment,” and also state the “average pain experienced,” throughout the procedure. Respondents will select the single number that best represents their pain intensity. Results from participants in the intervention arm will be compared to participants in the control arm.

Understanding the acceptability and effectiveness of VR in variations of patient demographics: Participants will be asked to state the following demographics – age, ethnicity, parity, menopausal status, previous attendances to colposcopy and previous treatments in colposcopy. Acceptability will be monitored by participants ongoing consent of using the VR headset. If a patient removes the headset before the colposcopy assessment is completed, this will be noted in the post procedural questionnaire and be noted that the patient did not find it acceptable. The demographics of this patient cohort will be reviewed to see how VR effects different patient demographics.

Feasibility and acceptance of intervention from clinicians’ perspective: Following completion of the colposcopy assessment, the clinician will be asked to complete a short survey of their experience using VR. (Appendix 6c) These will be questions on a Likert scale from “strongly disagree” to “strongly agree”. Clinicians will be asked did they find it easy to use the VR in their clinic, did they find it beneficial to the consultation, did they find it easy to communicate with the patient during the consultation.

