Demographic characteristics will be explored for missing data and distribution abnormalities. Means and standard deviations will be used to characterise the sample. Analysis of covariance (ANCOVA) and non-parametric tests (Mann – Whitney) will be used to determine whether the VR intervention lead to a significant difference between baseline and follow up anxiety between control VR and control arm. Descriptive statistics (i.e. age, gender, ethnicity, previous attendance to colposcopy, menopausal status and parity) for the baseline values will be presented within each randomized controlled arm. P values will be used to estimate statistical significance for all analysis.

End of Study Definition

The end of study will be upon completion of the final visit of the last participant/volunteer enrolled in the trial.

Project Management Plan

PROJECT MANAGEMENT PLAN (with project milestones)			
Action	Timescale	Responsibility	Indicator / Outcome / Evidence
Develop protocol	Aug 23- Dec 23	Fellow and Supervisors	Creation of protocol to ensure robust methodology and outcome measures
Scoping exercise amongst service users	Oct 23- Dec 23	Fellow	Ensure in keeping with service users focus
Train staff on VR equipment	Oct 23 - ongoing	Fellow, Rescape	Train staff alongside Rescape to use equipment
Recruitment PPI work for patient information leaflets, questionnaires	Oct 23 - ongoing	Fellow, Research nurses	Approaching service users for feedback to ensure legibility
Begin recruitment of service users	March 24 – August 24	Fellow, Research nurses	Consenting and awareness
Begin trial and data collection	March 24 – August 24	Fellow, Research team, supervisors	Comparison of VR to standard care
Completion of data collection and writing up	Aug 24 – Dec 24	Fellow, Supervisors	Writing up analysis
Dissemination of information	Jan 25 – Aug 25	Fellow, supervisors	Conference presentations, publications

Oversight and monitoring

Composition of the coordinating centre

[name] (Principal investigator) *Clinical Research Fellow Gynaecological Oncology*

- Design and conduct of “Mind over Cervix”.
- Preparation of protocol and revisions
- Chair of steering group

- Overall responsibility for study milestones
- Preparation of case report forms (CRFs)
- Managing, monitoring and ensuring integrity of collaborative relationships

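### The primary variable is not fixed: the plan points both to the post-procedure STAI score and to the change from baseline, and names neither the ANCOVA covariate nor the variable for the Mann-Whitney test

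*Combined protocol and SAP*

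**What the plan says.** All references are to the combined protocol and SAP.

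- **Registration data table, primary outcome:** a reduction in anxiety measured by STAI.
- **Outcomes, Primary outcome:** the entry opens by speaking of change in anxiety on the STAI and says that pre-procedure forms establish a baseline. It then states: "The comparison will be performed from the post procedure paper questionnaires from both arms of the study".
- **Plans for assessment and collection of outcomes, Primary outcome:** of the baseline form it says "This will be compared to the post procedural questionnaire (Appendix 6b) with the same questions". A comparison between the arms follows.
- **Statistical methods:** ANCOVA and Mann-Whitney are to determine whether VR leads to "a significant difference between baseline and follow up anxiety between control VR and control arm". No covariate is named, Mann-Whitney is not tied to post scores or to change scores, and neither test is given the lead.
- **Sample size:** "For the calculation the significance level of 0.05 and power of 0.8 were used along with a Cohen's d of 0.5". The text adds that "the calculations used are based on ANCOVA (continuous) and the Mann-Whitney test (ordinal") and that "Both results suggest a sample size of 64 participants in each group (128 in total"). It gives no SD, no correlation and no variable for d.

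**The concern.** The post-procedure score and the change from baseline are different variables. Unless the analysis adjusts for baseline, they have different variances, different test statistics and different P values. One section sends the analyst to the first and another to the second, and both cannot be followed in an unadjusted analysis.

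The trial is open-label and the outcome is self-reported, so the primary variable should be settled before any data are seen. As written, the choice could be made afterwards. It is also not fixed whether the headline estimate is a difference in post-procedure scores or a difference in mean reductions, and the planned power cannot be attached to either.

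**Working it through.** **Inputs from the documents.** Significance level 0.05, power 0.80, d = 0.5, 64 per arm (Sample size); 1:1 allocation (Implementation).

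**Assumed, because the documents do not give them.** Equal pre and post SDs; baseline-to-post correlation r from 0.3 to 0.7; two-sided testing; normal scores.

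**1. The plan's own figure.** A two-sided two-sample t-test at d = 0.5 needs 63.77, so 64 per arm, with power 80.1% at 64. A two-group F-test with f = 0.25, which is ANCOVA with no gain from a covariate, needs 127.5, so 128 in total. A one-sided test needs 51 per arm and does not match. The stated 64 is therefore the size for an unadjusted two-sided comparison of means. It holds for whichever variable d is standardised on. (For Mann-Whitney under normality the same inputs give 63.77 × π/3 = 66.8, so 67 per arm; that is a separate matter and nothing below rests on it.)

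**2. How the variables relate.** With post-score SD = 1:
- SD of change = √(2(1 − r))
- residual SD after adjusting for baseline = √(1 − r²)

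At r = 0.3 these are 1.183 and 0.954; at r = 0.7 they are 0.775 and 0.714.

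**3. Power at 64 per arm, under each reading of d.** If d = 0.5 is in post-score SDs, the standardised effect is 0.5/√(2(1 − r)) for change and 0.5/√(1 − r²) for ANCOVA. If d is in change-score SDs, it is 0.5·√(2(1 − r)) for the post score, and that value divided by √(1 − r²) for ANCOVA.

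| r | d in post SDs: post | change | ANCOVA | d in change SDs: change | post | ANCOVA |
|---|---|---|---|---|---|---|
| 0.3 | 80.1% | 66.0% | 83.7% | 80.1% | 91.3% | 93.6% |
| 0.5 | 80.1% | 80.1% | 90.0% | 80.1% | 80.1% | 90.0% |
| 0.7 | 80.1% | 95.2% | 97.6% | 80.1% | 58.5% | 86.1% |

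The unadjusted powers coincide at r = 0.5. Either side of that, which variable departs from 80% depends on a basis for d that the plan does not state.

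**4. How often the two variables disagree.** Simulation of 4,000 trials per r, 64 per arm, true effect 0.5 post-score SD, each test at two-sided 5%:

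| r | t-test, post against change | Mann-Whitney, post against change |
|---|---|---|
| 0.3 | 27% | 28% |
| 0.5 | 23% | 25% |
| 0.7 | 20% | 22% |

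In the same simulated trials, ANCOVA with baseline as covariate gave the same treatment effect for post and change (largest difference about 1e-15, which is rounding).

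**5. Type I error if either variable may supply the claim.** Under no effect, the unadjusted post and change statistics have correlation √((1 − r)/2): 0.592 at r = 0.3 and 0.387 at r = 0.7. The probability that at least one exceeds 1.96 in absolute value, from the bivariate normal, is 8.8% at r = 0.3, 9.1% at r = 0.5 and 9.4% at r = 0.7.

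**The case against.** The strongest reply is that ANCOVA is a named method and baseline STAI, collected before randomisation, is its natural covariate. With that covariate, post and change give one treatment effect and one P value, and the figures in steps 4 and 5 no longer apply. This is correct, and it limits the point to unadjusted comparisons. It does not dispose of the point: no section names the covariate, and Mann-Whitney, named for the same question, takes none, so its input must be chosen.

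A second reply is that the wording is loose rather than cleanly contradictory. That stands in part. The Outcomes entry itself begins with change, and the data-collection section can be read as a post-score comparison that takes baseline into account. The conflict is therefore not a tidy split with one section on each side. But the sentence in Outcomes on where the comparison is made and the sentence in Statistical methods on what is tested still name different variables.

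A reader might also infer that the 80% power fits only one of the two variables, or that a change-score analysis is underpowered. The documents do not support this. They tie d = 0.5 to neither variable and give no correlation, and step 3 shows that the variable short of 80% switches with the reading of d.

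**Conclusion.** The point holds in limited form. The primary variable, the ANCOVA covariate and the Mann-Whitney variable are all left open, and the sections cannot all be followed with an unadjusted test. Under the assumptions in the working, the choice of variable changes the significance verdict in about one trial in four to five, and free choice between the two nearly doubles the nominal 5% error. These sizes depend on the assumed r and apply only to Mann-Whitney or another unadjusted comparison. The power statement is undefined rather than shown to be wrong. The change should be made before any outcome data are examined.

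**What to change.** Use one definition in the registration data table, Outcomes, Plans for assessment and collection of outcomes, and Statistical methods: the primary analysis is the between-arm difference in post-procedure STAI, estimated by ANCOVA with baseline STAI as covariate, and this analysis decides the primary claim. Run Mann-Whitney as a sensitivity analysis on the same post-procedure score. Mean change per arm may be reported descriptively. In Sample size, state which SD the d = 0.5 refers to; the sponsor must supply this, since the documents do not imply it.

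With 64 per arm and the assumed r of 0.3 to 0.7, the adjusted analysis has power of 84% to 98% if d is in post-score SDs and 86% to 94% if it is in change-score SDs. The cost is wording only, with no extra patients or data. The sponsor gives up the freedom to use the unadjusted change score as primary.

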Study type	
Interventional
 
Allocation: randomized
 
Intervention model: parallel assignment
 
Masking: non blinded
 
Primary purpose: anxiety reduction
 
Phase I

Date of first enrolment	TBC
Target sample size	141
Recruitment status	Awaiting ethical approval
Primary outcome(s)	Reduction in anxiety experienced by biological females attending for outpatient colposcopy as measured by STAI (state trait anxiety index)

Key secondary outcomes
	
Reduction in pain experienced by biological females attending for outpatient colposcopy as measured by numerical rating scores (NRS)
 
Understanding the acceptability and effectiveness in terms of reducing anxiety of VR interventions within the procedural groups and how these might vary as a function of different patient demographics.
 
Feasibility and acceptance of intervention from clinicians' perspective
 
Does the introduction of VR have an impact on patients' attendance to follow up appointments

--------------------------------------	---

Names protocol contributors

Main Sponsor: University of Ulster

Funders: N/A

Study Coordination Centre: Queen Elizabeth Hospital, [name]

IRAS

Study Management Group

Chief Investigator: [name]

Primary Investigator: [name]

Study Supervisor: [name]

Co-Investigators: [name], [name],

Statisticians: [name], [name] (Queens University, Belfast)

Study Management: Ulster University

Study Coordination Centre: Queen Elizabeth Hospital, Gateshead.

Funding: This study is part of a research fellowship. The medical devices company Rescape have provided the headsets for use in research free of charge but have had no role in the design of the study and will not have a role during its execution, analyses, interpretation of data or decision to submit results. It will have no access to or ownership over any patient data collected during this study.

General and clinical queries, supply of study documents and collection of data please contact [name] (Clinical Research Fellow, Chief Investigator) ([contact]) or [name] (Consultant Gynaecologist, Study Supervisor) ([contact])

Issue Date: 18.04.24

Protocol Amendment Number: 05

Author(s): V.B, C.M, N.R

Abstract

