Participants will be randomly assigned to either control or VR intervention group by patient selection of a choice of two opaque envelopes. One envelope will instruct participant to be part of the control arm, one envelope will instruct the participant to be part of the intervention arm. The envelopes will be blinded to the researcher who provides the envelopes for the patient to choose.

Concealment mechanism Potential patients will be invited to take part in the trial prior to knowledge of what arm they will be involved in. They will be asked to complete the initial questionnaire to get a baseline STAI score before randomisation. They will be randomly allocated by patient choice of an opaque sealed envelope that will contain if they are to join the intervention or control arm. These envelopes will be blinded to the research team until after the patient selection.

Implementation All patients who consent for participation and meet the inclusion criteria will be randomized. Randomization will occur following the consent process and initial questionnaire. A member of the research team will be responsible for providing the sealed opaque envelopes for randomisation. Sealed identical opaque envelopes will be made ahead of time by the research team on a 1:1 ratio.

Assignment of interventions: Blinding

Who will be blinded?

Due to the nature of the intervention, the study team felt it is not possible to blind participants or assessors once the study arm has been allocated. Participant questionnaire results will be concealed from the assessor at point of contact.

Data collection and management

Plans for assessment and collection of outcomes

Primary outcome

Anxiety reduction: Anxiety will be measured using the state trait anxiety index (STAI) STAI was chosen as it is a well-known measure of trait and state anxiety. It is considered the “gold standard” of measuring preoperative anxiety and its reliability and validity have been well reported in literature. (33,34) State items include “I feel upset,” “I feel frightened,” “I feel nervous,” “I am jittery” and I feel confused.” Patients respond with a numerical value of 1 to 4 with 1 meaning “not at all” and 4 meaning “very much so”. (27,28)

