A pseudo-anonymised database will be prepared for analysis within the Trust for transfer for analysis at Queens University Belfast. The data for use outside the NHS will be prepared in a manner that will not allow the potential identification of individuals by combinations of data, for example, by using appropriate and ethnic group grouping that do not risk identification of individuals and anonymising all but the highest-level geographical data. Team members carrying out test accuracy and analysis will have no access to personal identifiable data.

Data generated from the research project will be stored for 10 years on NHS and/or University computers in an anonymised manner and after any patient identifiable information is removed. Access to these computers will be password protected and only by members of the research team.

Confidentiality

Confidentiality will be maintained at all times and be under the supervision of the primary investigator (VB). Members of the local site research team will have NHS

contracts with the obligation to follow all relevant NHS codes of practice and guidance. They will maintain required relevant training including NHS information governance, data security and GCP.

All participants will be allocated a number from 1-141 on their enrolment into the trial. The PI will have a separate data log to enable correlation between clinical data and study data. No other members of the team will have access to it and it will be stored on a password protected trust computer.

Questionnaires collected for analysis will be anonymous and results will be added to a password encrypted Excel, retaining the anonymity of the patients. This anonymous data will be sent via a secure link to the statisticians for analysis. No identifiable patient information will leave the hospital trust information system.

Statistical methods

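### Minor, drop-out allowance only: a target of 141 keeps the required 128 evaluable participants with up to 9.2% loss, not the stated 10%

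*Combined protocol and SAP*

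**What the plan says.** The Sample size section gives its inputs as follows: "For the calculation the significance level of 0.05 and power of 0.8 were used along with a Cohen's d of 0.5". It bases the calculation on ANCOVA for continuous outcomes and the Mann-Whitney test for ordinal ones, and reports one answer for the two: "Both results suggest a sample size of 64 participants in each group (128 in total". The allowance for loss follows: "We have added on a 10% drop out rate which brings the total sample size to 141".

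The same total appears in two other places. The summary table at the front gives 141 in the row "Target sample size", and the Confidentiality section says "All participants will be allocated a number from 1-141 on their enrolment into the trial". So 141 is the fixed enrolment figure throughout, and a 10% drop-out rate is the only reason given for going above 128.

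**The concern.** A drop-out rate is ordinarily the share of recruited participants who provide no usable outcome. On that meaning, a total described as covering 10% drop-out should leave at least the required 128 when 10% of those recruited are lost. Adding 10% of 128 does not quite do this, because 10% of the larger recruited number exceeds 10% of the evaluable number.

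What is at stake is the accuracy of a stated figure. The sponsor intends to publish the protocol, and readers will take 141 to mean 128 evaluable participants with full cover for 10% loss. A loss inside the plan's own allowance would put the trial one participant below its own requirement.

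**Working it through.** **Inputs, all from the combined protocol and SAP**

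- Significance level 0.05, power 0.80, Cohen's d 0.5 (Sample size). Sidedness is not stated.
- Required evaluable number: 64 per group, 128 in total (Sample size).
- Drop-out: 10% (Sample size).
- Allocation 1:1 (Implementation): "Sealed identical opaque envelopes will be made ahead of time by the research team on a 1:1 ratio".
- Recruitment target: 141 (Sample size, summary table, Confidentiality).

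**Step 1. Reproduce the base figure.** A two-sample t calculation with d = 0.5, two-sided 0.05 and power 0.80 gives 63.77 per group, rounded up to 64, so 128 in total. This matches the plan. A one-sided test would need only 50.15, so 51 per group, which is why a two-sided test is assumed below. The base of 128 is not in dispute.

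**Step 2. Reproduce the inflated figure.** N × (1 + d), where d here is the drop-out rate: 128 × 1.10 = 140.8, rounded up to 141. This matches exactly and shows how the target was obtained.

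**Step 3. Apply a 10% loss to those recruited.** 141 × 0.90 = 126.9. In whole people:

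| Losses from 141 | Share lost | Evaluable |
|---|---|---|
| 13 | 13/141 = 9.2% | 128 |
| 14 | 14/141 = 9.9% | 127 |

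The largest loss that keeps 128 is therefore 9.2%.

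**Step 4. Find the total that covers a full 10%.** N / (1 − d) = 128/0.90 = 142.2, rounded up to 143, or 144 for equal arms. Check: 142 × 0.90 = 127.8, just short; 143 × 0.90 = 128.7, enough. Starting from the unrounded base does not rescue 141: 2 × 63.77/0.90 = 141.7, so 142.

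**Step 5. Size the effect on power.** ANCOVA power comes from the noncentral t distribution with N − 3 degrees of freedom and noncentrality [0.5/√(1 − r²)] × √[n₁n₂/(n₁ + n₂)], two-sided 0.05, where r is the correlation between baseline and post-procedure STAI. With r = 0 the noncentrality is 0.5 × √32 = 2.828 at 64/64 and 0.5 × √(4032/127) = 2.817 at 64/63.

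| Evaluable (arm/arm) | r | Power |
|---|---|---|
| 64/64 | 0 | 80.1% |
| 64/63 | 0 | 79.8% |
| 65/62 | 0 | 79.8% |
| 64/63 | 0.1 | 80.2% |
| 64/63 | 0.2 | 81.4% |
| 64/63 | 0.3 | 83.4% |

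The documents give no value of r, so the range 0 to 0.3 is an assumption. With no correlation the cost of falling to 127 is 80.1 − 79.8 = 0.3 percentage points. A correlation of about 0.1 removes it.

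**The case against.** The strongest reply is that the sentence is true as literally worded. It says 10% was added on, 10% added to 128 gives 140.8, and 141 follows. The section never promises in so many words that 128 will remain after 10% of those recruited are lost, and the three places that give the total agree. This stands as an explanation of where 141 comes from. It does not make 141 an allowance for 10% drop-out, which is what the sentence calls it: a drop-out rate is a rate among those recruited, and on that meaning 14 losses are within the allowance and leave 127.

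The second reply is that the difference does not matter in practice, and this stands in full. The gap is two participants (143 against 141). The power cost is 0.3 points and arises only if baseline anxiety is essentially uncorrelated with post-procedure anxiety, although the same STAI questions are asked at both times and ANCOVA is planned. Participation lasts only as long as the clinic appointment, and the protocol does not expect retention to be a significant factor.

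A reader might go further and infer that the trial is underpowered, that recruitment must rise to 143 or 144, or that the base of 64 per group is wrong. The documents support none of these. The base reproduces from the stated inputs, the shortfall at 10% loss is one evaluable participant, and the planned baseline adjustment can be expected to recover more than that.

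**Conclusion.** The point holds at the lowest severity and concerns the drop-out allowance only. The target of 141 retains 128 evaluable participants with up to 13 losses (9.2%). At the stated 10% about 127 remain, and power falls from 80.1% to 79.8%.

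The retention figures follow from the plan's own numbers and need no assumption beyond reading a drop-out rate as a share of those recruited. The power figures also rest on a two-sided 0.05 test, which is inferred because it reproduces 64 per group, and on zero baseline correlation, which is the least favourable case in the range shown. This is a correction to a stated figure and not a threat to the trial.

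**What to change.** Keep recruitment at 141 and replace the sentence on drop-out in the Sample size section with wording such as:

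> 141 will be recruited, which retains 128 evaluable with up to 9.2% loss; at 10% loss about 127 are evaluable (power about 79.8% before any gain from baseline adjustment).

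The cost is one sentence. The summary table and the participant numbering stay as they are, and nothing changes in recruitment, allocation or analysis.

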- There are no addition exclusion criteria as per the manufacturers instructions

Inclusion Criteria (Staff)

- Have completed colposcopy training and be a registered member of the British Society of Colposcopy and Cervical Pathology (BSCCP)
- Have completed informed consent.

Exclusion Criteria (Staff)

- The denial or withdrawal of informed consent.
- Trainee colposcopist performing clinic.

Interventions

Explanation for the choice of comparators

Biological females are offered a colposcopy appointment depending on the results of their routine cervical screening. Screening occurs every 3 years from age 25 until 49, and then 5 yearly from age 50 to 64. Cervical screening looks for HPV initially, and if this is found then cytology is performed on the specimen. If abnormal cells are found, patients are referred to colposcopy for further investigation. Here, the cervix is examined in great detail for any concerning changes. If there are areas of concern, it may require a LLETZ treatment to remove part of the cervix to prevent it from developing into cancer.

Despite the undeniable importance of colposcopy in women's' health, it is known to be a time of very high anxiety. In line with NHS values, we need to try to improve patients experience of colposcopy and try novel methods of reducing their anxiety. VR has been shown to be an effective and safe intervention in other outpatient procedures to reduce anxiety, it has not yet been investigated during outpatient colposcopy procedures. (15,18,19,20)

Intervention description

Once consented and enrolled in the trial, participants will then be asked to complete the study questionnaire (Appendix 4) which will be a paper-based format. This will allow measurement of baseline and state anxiety and anticipated pain. We will collect this data prior to randomisation of the participant into either arm of the trial. Patients will then be randomly allocated to either the VR intervention arm or the standard procedure arm. The clinician taking consent will ask the service to choose from two opaque, blank envelopes that will contain inside if they are to be enrolled in the intervention or control arm. The envelopes will be blinded to both the clinician and the patient prior to selection.

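### Each patient picks between two blank envelopes, and the available text describes no allocation list, envelope numbering or allocation record, so the allocation could not be audited

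*Combined protocol and SAP*

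**What the plan says.** The section on sequence generation and concealment says that participants are "randomly assigned to either control or VR intervention group by patient selection of a choice of two opaque envelopes". One envelope assigns control and the other assigns VR. The Intervention description adds that the envelopes carry no marking: "The clinician taking consent will ask the service to choose from two opaque, blank envelopes".

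On preparation, the Implementation paragraph says: "Sealed identical opaque envelopes will be made ahead of time by the research team on a 1:1 ratio". On concealment: "These envelopes will be blinded to the research team until after the patient selection". Consent and the baseline questionnaire come before the pick.

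On numbering, the Confidentiality section says: "All participants will be allocated a number from 1-141 on their enrolment into the trial". It also gives the principal investigator a data log linking clinical and study data. Neither the number nor the log is described as tied to an envelope or an arm.

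The Blinding section accepts that "it is not possible to blind participants or assessors once the study arm has been allocated". The primary outcome is STAI from paper questionnaires that patients complete.

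**The concern.** A pre-generated list with numbered envelopes fixes the arm of each successive participant before that person is enrolled. Anyone holding the list can later compare what was planned with what happened.

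Here nothing is fixed beforehand. The heading announces sequence generation, but the text under it describes a stock of envelopes and a choice, not a sequence. At every pick both arms are on the table. If a patient disappointed with control were allowed to pick again, the resulting record would look like any other. The weakness therefore lies after the pick, not before it.

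What is at stake is the ability to show that the arms compared are the arms that chance produced. If the patients moved differed systematically from the rest, the comparison would be biased, and no described document would show it.

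**Working it through.** **Inputs from the protocol.** Total 141, ratio 1:1, two-sided 5% level assumed (sidedness is not stated), design effect d = 0.5. The plan's own figure reproduces: a two-sample t-test with d = 0.5, alpha 0.05 and power 0.80 needs 63.8, so 64 per arm or 128; 128 × 1.10 = 140.8, so 141. The point does not rest on this figure.

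**Step 1. Could arm totals reveal swaps?** Assume a fresh pair for each patient, so picks are independent with probability 0.5. The text does not say whether pairs are fresh or drawn from a common stock.
- Expected VR count: 141 × 0.5 = 70.5. SD: √(141 × 0.25) = 5.94.
- Exact binomial 2.5th and 97.5th percentiles: 59 and 82.
- Exact two-sided 5% test: flag if the VR count is 58 or fewer, or 83 or more (true size 0.043).
- With k swaps from control to VR, the VR count is X + k, with X ~ Binomial(141, 0.5):

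| One-way swaps k | P(flag) |
|---|---|
| 0 | 0.043 |
| 2 | 0.055 |
| 5 | 0.121 |
| 10 | 0.368 |

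Even 10 swaps give an expected VR count of 80.5, inside the chance range.

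**Step 2. How large could the bias be?** The documents give no swap rate, so this is illustration only. Assumptions:
- no true average effect;
- k patients drawn at random from the top quarter of an unmeasured trait (say, keenness for VR) among those who drew control, about 17.5 patients, are moved to VR;
- the trait is uncorrelated with baseline STAI, and its correlation r with post-procedure STAI is 0.2 to 0.5;
- baseline and post-procedure STAI correlate 0.5, and the ANCOVA adjusts for baseline STAI.

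The mean of a standard normal trait in its top quarter is 0.3178 / 0.25 = 1.271. The approximate bias towards VR, in SD units, is then:
- trait acts in both arms: 1.271 × r × k × [1/(70.5 + k) + 1/(70.5 − k)];
- trait acts only under VR: 1.271 × r × k / (70.5 + k).

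Example with k = 2, r = 0.5, both arms: 1.271 × 0.5 × 2 = 1.271; 1.271/72.5 + 1.271/68.5 = 0.0175 + 0.0186 = 0.036.

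The formulas agree with simulated bias to within about 0.003 SD. Type I error comes from simulation (20,000 runs per cell for 5 and 10 swaps; 8,000 per cell for 1 and 2).

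| Swaps | Share of keen controls | Bias, VR only | Bias, both arms | Type I error, VR only | Type I error, both arms |
|---|---|---|---|---|---|
| 0 | 0% | 0 | 0 | 5% | 5% |
| 1–2 | 6–11% | at most 0.02 | at most 0.04 | about 5% | 5–6% |
| 5 | 29% | 0.02–0.04 | 0.04–0.09 | 5–6% | 6–9% |
| 10 | 57% | 0.03–0.08 | 0.07–0.18 | 6–8% | 8–23% |

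**Step 3. Would blocking be a free improvement?** No. With independent allocation a recruiter guesses the next arm correctly 50% of the time. With randomly varying blocks, a recruiter who has seen the past arms and guesses the under-represented one is right about 72% of the time (sizes 2/4), 70% (2/4/6), 69% (4/6) or 68% (4/6/8). These come from simulation at N = 141; the block sizes are assumptions.

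**The case against.** The strongest reply is that the method is good where it matters most. Envelopes are sealed, opaque and identical, contents are hidden until the pick, and consent and baseline come first. No one can predict the next arm. All of this stands, so a reader who infers that allocation is unconcealed, or not random, goes beyond the text.

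Second, nothing suggests that swapping will happen. A swap needs a staff member to permit it, and controls are offered a headset trial afterwards, which lowers the incentive. This also stands. The 23% type I error is not a forecast: it needs 10 swaps, all one way, more than half of the keen controls moved, and a trait acting in both arms that predicts the outcome as well as baseline STAI does.

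Third, a record may exist. Part of the oversight text and the appendices, including the deviation log, were not available, and the contents of the SOP file, the data log and the case report forms are not shown. A reader might conclude that no allocation record is kept; the documents do not support that. But a record made after the pick would still have no pre-set list to be checked against.

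Fourth, a reader might blame the envelopes for the risk from open-label, self-reported anxiety. Expectation effects would be the same under a perfect sequence and are not part of this point.

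**Conclusion.** The point holds as a gap in auditability. On the available text, allocation is concealed and fair before the pick but cannot be verified after it, and arm totals cannot fill the gap.

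The likely consequence is small: type I error stays at about 5 to 6% with 1 or 2 swaps. It would become material only with many one-way swaps: 5 to 9% with 5 and 6 to 23% with 10. The largest bias in the table, 0.18 SD, compares with a design effect of 0.5 SD. These sizes rest on the assumed trait model, independent picks and ANCOVA adjustment for baseline STAI.

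Confidence is high that no sequence or numbering is described, and lower that no allocation record exists elsewhere. The change should be made because it is cheap and an unverifiable allocation cannot be repaired afterwards; it is not a finding of subversion.

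**What to change.** Replace the two-envelope pick, before enrolment begins, as follows:

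1. The trial statisticians generate and retain a 1:1 simple (unblocked) randomisation list. They are at a separate institution: the database is to be "prepared for analysis within the Trust for transfer for analysis at Queens University Belfast".
2. An existing team member who does not recruit fills sequentially numbered, opaque, sealed envelopes from the list.
3. After consent and the baseline questionnaire, staff write the study number, date and time on the next envelope, then open it and enter it in an allocation log.
4. The log is checked against the retained list.

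If an allocation record already exists in a document not shown, the protocol should cite it; the list and numbering would still be needed.

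The cost is a short amendment, one computer-generated list, one envelope per participant and a log. There are no extra patients or visits. There are two downsides: patients no longer choose an envelope, and a numbered stack must be kept secure so that it is not opened ahead.

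Blocking is not needed for audit. If the sponsor wants balanced arms, it should accept explicitly the 68 to 72% predictability that small varying blocks bring in this unblinded, single-site trial, against 50% with independent allocation.
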